2.4 Secondary outcomes

Secondary outcomes are listed in the study protocol as:

- (1) Time from surgery to hospital discharge
- (2) Pain scores in the first two days post-surgery
- (3) Adverse health events to one year
- (4) Proportion and time to uptake of adjuvant treatment
- (5) Proportion of patients upstaged to pN2 disease
- (6) Overall and disease-free survival to one year
- (7) Proportion of patients who undergo complete resection (i.e. R(0) resection) during the procedure
- (8) Proportion of patients who experience prolonged incision pain (defined as the need of analgesia > 5 weeks post randomisation that was not being taken pre-operatively)
- (9) Generic and disease-specific HRQoL: EORTC QLQ-C30, QLQ-LC13 and EQ5D to one-year (measured at 2 weeks, 5 weeks, 3 months, 6 months and 12 months post-randomisation)
- (10) Resource use to one year (measured for the duration of post-operative hospital stay until discharge, and at 5 weeks, 3 months, 6 months and 12 months post-randomisation)

Additional secondary outcomes:

- (11) Proportion of patients upstaged to pN1 disease

As stated in section 1.1, outcome (10) is not covered in this SAP. Outcome (11) is not specified in the protocol but was added at the request of the chief investigator before any knowledge of the accruing data.

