Upstaged to pN2	YES: if pathological disease stage of primary tumour = N2 NO: if pathological disease stage of primary tumour = N0 OR N1 NOT CANCER: no cancer, sample benign MISSING: otherwise

6. Overall and disease-free survival to 1 year

Both overall and disease-free survival to 12 months will be compared between groups.

New variable	Rules
Time to death (days)	(Death date – randomisation date)
Death censor variable	YES: if patient did not die before the end of follow-up NO: if patient died before the end of follow-up MISSING: otherwise
Time to disease progression (days)	(Date of earliest disease recurrence – randomisation date)
Disease progression censor variable	YES: if patient did not have disease progression before the end of follow-up NO: if patient had disease progression before the end of follow-up MISSING: otherwise

7. Proportion of patients who undergo complete resection during the procedure

Completeness of the resection will be defined as follows:

New variable	Rules
Complete resection	YES: if resection completeness = R0 (no residual tumour) NO: if resection completeness = R1 (microscopic residual tumour) OR R1 (other than microscopic residual tumour) OR R2 (macroscopic residual tumour) MISSING: otherwise

8. Proportion of patients who experience prolonged incision pain

Prolonged incision pain is defined as the need for analgesia after 5 weeks post-randomisation.

New variable	Rules
Prolonged incision pain	YES: if patient continuously prescribed analgesia until after 5 weeks post-randomisation that was not being taken preoperatively NO: if patient not continuously prescribed analgesia until after 5 weeks post-randomisation OR patient continuously prescribed analgesia that was administered pre-operatively until after 5 weeks MISSING: otherwise

9. General and disease-specific HRQoL: EORTC QLQ-C30, QLQ-LC13 and EQ5D to 1 year

The QLQ-C30, QLQ-LC13 and EQ5D questionnaires are completed at baseline, 2 weeks, 5 weeks, 3, 6 and 12 months. Details for how to derive the overall and sub-scale scores for these three questionnaires can be found below in the respective tables. The EORTC core questionnaire and associated modules scoring manual will be used to derive the QLQ-C30 and QLQ-LC13 scores ⁽¹⁾.

New variable – QLQ-C30	Rules
Global health status (QL2) raw score	At each time point: = mean of question 29 and 30, if both non-missing MISSING: otherwise
QL2 overall score	At each time point: = $[(\text{QL2 raw score}-1)/6] * 100$

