6.2.2 Analysis models

All outcomes listed in the study protocol will be presented as per the template tables **Table T11 to T18**. General methods of presentation and assessing treatment effects are outlined below. For all treatment comparisons, the open lobectomy group will be the reference group. Details specific to each outcome are described as appropriate.

Each outcome will be considered under a certain data type, as outlined in the table below:

Date type	Outcomes
Binary	Proportion of patients receiving adjuvant treatment Proportion of patients who undergo complete resection during the procedure Proportion of patients who experience prolonged incision pain Any in-hospital adverse event Any in-hospital serious adverse event
Categorical	Proportion upstaged to pN1 disease after the procedure Proportion upstaged to pN2 disease after the procedure
Time to event	Time from surgery to hospital discharge Time to uptake of adjuvant treatment Overall survival Disease-free survival
Longitudinal	Physical function (primary) Pain scores in the first two days post-surgery HRQoL (QLQ-C30, QLQ-LC13, EQ5D)

Each type of data will be summarised and compared between the groups according to the following:

- **Binary outcomes** will be presented as numbers and percentages of patients in each treatment group. Outcomes will be compared between treatment groups using generalised linear models, with treatment comparison estimates presented as adjusted risk ratios (RR) and risk differences (RD) with 95% confidence intervals (95% CI). Formal statistical comparisons of treatment effects will only be performed if more than ten patients in total experience the outcome (with at least one event in each treatment group).
- **Categorical outcomes** will be presented as numbers and percentages of patients in each treatment group in each category. Outcomes will be compared between treatment groups using multinomial logistic regression, with treatment comparison estimates presented as adjusted RR and 95% CI.

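### The derivation of prolonged incision pain can code one patient both YES and NO, scores early deaths as NO, and adds a continuity condition that the stated definitions lack

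*SAP*

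**What the plan says.** The SAP describes this outcome in three places.

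- Section 2.4, item 8, has it "defined as the need of analgesia > 5 weeks post randomisation that was not being taken pre-operatively".
- The sentence that opens item 8 in section 5.2 reads "Prolonged incision pain is defined as the need for analgesia after 5 weeks post-randomisation". It does not set aside drugs already taken before surgery.
- The derivation table below that sentence gives the coding. The event is "YES: if patient continuously prescribed analgesia until after 5 weeks post-randomisation that was not being taken preoperatively". The non-event has two parts, either of which suffices: "NO: if patient not continuously prescribed analgesia until after 5 weeks post-randomisation", and "OR patient continuously prescribed analgesia that was administered pre-operatively until after 5 weeks". Anything else is missing.

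Section 6.2.2 lists "Proportion of patients who experience prolonged incision pain" among the binary outcomes, to be compared by risk ratio and risk difference. Table T13 has a row for it.

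**The concern.** A coding rule should place each patient in exactly one category, and that category should follow from the stated outcome. This rule fails on both counts.

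The second part of NO looks only at the pre-operative drug and does not ask whether a new one is also in use. Patients on both are foreseeable, since Table T4 records chronic pain syndrome as baseline history. With no order of precedence, two programmers working from this text could produce different datasets.

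The first part of NO is met by anyone whose prescription did not run past 5 weeks, for whatever reason. Death is one such reason, and it then counts as freedom from prolonged pain.

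Finally, the table replaces need with unbroken prescription. At stake is whether the row in Table T13 reports the outcome that section 2.4 names.

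**Working it through.** The SAP gives no rate, power or sample size for this outcome, so there is no figure to reproduce. The check is logical.

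**Set-up.** Take the pre-operative analgesic and any new analgesic separately. Each can be absent, stopped before 5 weeks, in use after 5 weeks but interrupted, or unbroken past 5 weeks. That gives 4 × 4 = 16 patterns for a patient followed past 5 weeks. Each cell shows the coding under the literal table.

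| Pre-operative drug | New: none | New: stopped before 5 weeks | New: in use after 5 weeks, interrupted | New: unbroken past 5 weeks |
|---|---|---|---|---|
| None | NO | NO | NO | YES |
| Stopped before 5 weeks | NO | NO | NO | YES |
| In use after 5 weeks, interrupted | NO | NO | NO | YES |
| Unbroken past 5 weeks | NO | NO | NO | YES and NO |

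**Events under each statement of the outcome.**

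- Section 5.2 opening sentence (any analgesic needed after 5 weeks): all patterns except those where both drugs are absent or stopped, 16 − 2 × 2 = 12.
- Section 2.4 (a new analgesic needed after 5 weeks): the last two columns, 2 × 4 = 8.
- Derivation table: the last column, 4, of which 1 is also NO.

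**Comparison of the table with section 2.4.** Four patterns are events by 2.4 but coded NO (third column of new-drug status). One is coded both ways (bottom right). The remaining 16 − 4 − 1 = 11 agree. No pattern falls outside both rules, so the missing category resolves none of the conflicts.

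**Comparison of the two definitions.** They differ in 12 − 8 = 4 patterns: a pre-operative drug is still in use and no new drug is. The pre-operative qualifier alone decides these.

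**Death before 5 weeks.** Such a patient was not prescribed analgesia up to and beyond 5 weeks. That satisfies the first part of NO. The missing category applies only when neither YES nor NO is met, so on the literal text it is not reached.

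**What a continuity condition would do to the estimates.** Suppose the rule captured the same fraction s of 2.4 events in both arms, with true rates p1 and p0. The risk difference becomes s × (p1 − p0), which is smaller. The risk ratio is (s × p1)/(s × p0) = p1/p0, which is unchanged. If s differs between arms, both are biased. The SAP gives no value for s, p1 or p0.

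The counts above are of logical patterns, not of patients.

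**The case against.** The strongest reply is that continuity is deliberate. The outcome is called prolonged and is attributed to the incision; requiring analgesia to run without a break past 5 weeks is a reasonable way to express both. On that view the sentences give the concept and the table makes it operational. This stands as a possibility, but the SAP does not say so.

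A reader might infer that every patient with interrupted or restarted analgesia is a true event wrongly coded. The documents do not support that, because they do not establish that later use is for incision pain. Nor do they support counting any new analgesic used at any time after 5 weeks. Follow-up runs to 12 months (section 3.1), so such a rule would take in drugs started months later for other reasons.

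A reader might also infer a definite loss of power. That would need event rates and a missed fraction, and the SAP has neither.

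On the overlap, one could read analgesia as the whole regimen rather than drug by drug. The qualifier about what was taken before surgery points to the drug-by-drug reading. The whole-regimen reading still leaves no rule for a patient on old and new drugs together.

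On deaths, one could argue that a patient with no status at 5 weeks is missing. That is a sensible intention, but not what the table says. It also has a consequence: under section 6.2.8, multiple imputation is considered once more than 5% of a single-time-point outcome is missing, and analgesic need would then be imputed for patients who had died.

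Whether the records can show interrupted or non-prescribed use is unknown. The schedule in section 4 has no row named for analgesia after discharge, and the case report forms are not shown.

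**Conclusion.** The point holds as a defect of derivation. The YES and NO rules are not mutually exclusive. Read literally, they score death before 5 weeks as the favourable outcome. They also carry a continuity condition that neither definition states, while the two definitions differ on pre-operative drugs. The overlap rests on reading analgesia drug by drug, and the point about deaths on reading the first part of NO as written.

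Continuity itself is not shown to be wrong; it is unstated where the outcome is defined. The size of the effect cannot be computed from the SAP, which gives no event rate, no share of patients on both kinds of drug and no count of early deaths. The primary outcome is untouched. Because this is a listed secondary outcome with a formal comparison, the rule should be corrected before the variable is derived.

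**What to change.** In section 5.2, item 8:

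- **YES** whenever an analgesic not taken before surgery meets the criterion past 5 weeks, regardless of any pre-operative drug that continues. YES takes precedence.
- **NO** only if the patient was observed past 5 weeks and did not meet YES because no analgesic, or only pre-operative ones, met the criterion.
- **Death or loss before 5 weeks** is not NO. Report early deaths separately by arm, do not impute them under section 6.2.8, and state that the comparison is then among patients alive past 5 weeks.

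Then make section 2.4, the opening sentence of 5.2 and the table agree on the pre-operative qualifier and on continuity. There are two ways to settle continuity. One is to write it into the definition, saying from when it is counted. The other is to drop it from the rule and fix an assessment window, for example use at the 5-week assessment that continues beyond it. Whichever is chosen, run the other coding as a sensitivity analysis if the records allow.

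The cost is a small change in derivation code and a documented amendment with re-approval, as section 1.2 requires. The sensitivity analysis depends on what the case report forms recorded, which should be checked first.

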5.3 Other variables

Details for any other variables which will be derived for use in any other figures or tables are given below:

New variable	Rules
Exclusion category	INELIGIBLE: any of the inclusion criteria are NO, or any of the exclusion criteria are YES NOT APPROACHED: patient is eligible, patient approached = NO DID NOT CONSENT: patient is eligible, patient approached = YES, patient consented = NO OTHER: patient is eligible, patient approached = YES, patient consented = YES, randomised = NO
Age at randomisation (years)	= (date of randomisation – date of birth)/365.25
Body mass index (BMI)	= weight (kg) / height (cm) ² * 10,000
Protocol deviation 1 – patient did not meet the study eligibility criteria but was randomised	YES: if patient was not eligible at screening but was randomised NO: if patient was eligible MISSING: otherwise

Protocol deviation 2 – patient did not undergo a lobectomy	
YES: if lobectomy = NO NO: if lobectomy = YES MISSING: otherwise

Protocol deviation 3 – patient received alternative allocation (only includes those who underwent a lobectomy)	
YES: if either:
 
 • Allocation = VATS AND lobectomy received = open • Allocation = open AND lobectomy received = VATS 
NO: if either:
 
 • Allocation = VATS AND lobectomy received = VATS • Allocation = open AND lobectomy received = open 
MISSING: otherwise

Protocol deviation 4 – more than four ports/incisions used	
YES: if more than four ports/incisions used during procedure NO: if less than four ports/incisions used during procedure MISSING: otherwise

Conversion from VATS to open	
YES: if allocated to VATS AND open lobectomy received NO: if allocated to VATS AND VATS lobectomy received MISSING: otherwise

Benign disease on frozen section	
YES: if frozen section = YES AND frozen section diagnostic = YES AND malignancy confirmed = NO NO: if either:
 
 • Frozen section = NO • Frozen section = YES AND frozen section diagnostic = NO • Frozen section = YES AND frozen section diagnostic = YES AND malignancy confirmed = YES 
MISSING: otherwise

Benign disease on post-operative pathology	
YES: if post-operative pathology = benign NO: if post-operative pathology = cancer MISSING: if benign disease on frozen section = YES

Blinding indices	Blinding indices will be calculated for both patients (2 days post-surgery and discharge) and nurses (discharge, 5 weeks and 12 months) using the method proposed by Bang et al ⁽²⁾ .
Duration of drain	= drain of drain removal – operation date
FEV ₁ , FVC expected values	Expected values are calculated using the method proposed by Quanjer et al ⁽³⁾ .
TLco expected values	Expected values are calculated using the method proposed by Stanojevic et al ⁽⁴⁾ .
FEV ₁ , FVC, TLco % predicted	= (observed value/expected value)*100

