3.3 Protocol deviations

The following types of protocol deviation will be considered:

- Patient did not meet the study eligibility criteria but was treated in the study.
- Patient did not undergo lobectomy
- Patient received the alternative intervention to that they were allocated (only includes patients who underwent a lobectomy)

Note it may be possible for patients to be classified as a protocol deviation for more than one reason.

The frequency of each type of deviation will be tabulated by treatment allocation (see **Table T1**).

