Figure F2 Predicted and actual recruitment

[figure not shown]

Table T1 Protocol deviations

	Randomised to open (n=XX)		Randomised to VATS (n=XX)		Overall (n=XX)	
	n	%	n	%	n	%
Any protocol deviation						
Patient ineligible but treated in the study						
Patient did not undergo lobectomy						
Patient received the opposite intervention to that they were allocated*						

Notes: *only includes patients who underwent a lobectomy

Table T2 Details of conversions from VATS to open surgery

	Randomised to VATS (n=XX)	
	n	%
Converted from VATS to open		
Reason for conversion		
Technical problems		
Equipment malfunction		
Failure to progress		
Poor visualisation		
Anatomical problems		
Absent or thick fissure		
Calcified peri-arterial nodes		
Chest wall invasion		
Diffuse pleural adhesion		
Requirement for sleeve resection		
Oncological problems		
Discovery of N2 tumours		
Invasion of the artery		
Invasion of the parietal pleura		
Margin extension		

Table T3 Withdrawals

	Randomised to open (n=XX)		Randomised to VATS (n=XX)		Overall (n=XX)	
	n	%	n	%	n	%
Any withdrawal						
Timing of withdrawal						
Post-consent pre-randomisation						
Post-randomisation but before surgery						
After surgery						
Reason for withdrawal						
Clinician's advice						
Surgery no longer appropriate						
Patient no longer eligible						
Other						
Patient's decision						
Referral to another centre						

Patient changed their mind about the study

Patient no longer wants surgery

Refused to give reason

Other

Admin/logistical reasons

Surgeon changed

Other

Further details

Withdrawn from follow-up

Notes:

Other reasons will be provided in footnotes

Table T4 Baseline demographic and clinical characteristics

	Randomised to open (n=XX)	Randomised to VATS (n=XX)	Overall (n=XX)
Baseline characteristics			
Age (years)			
Sex	Male		
	Female		
Smoking status (ever smoked)			
Ethnicity	White or Caucasian		
	Black / Black British		
	Mixed / multiple ethnic groups		
	Asian / Asian British		
	Other ethnic group		
Clinical TNM8 stage			
T1a			
T1b			
T1c			
T2a			
T2b			
T3			
N0			
N1			
M0			
Location of primary tumour			
Left upper lobe			

Left lower lobe
Right upper lobe
Right middle lobe
Right lower lobe
Other

Baseline clinical measures

BMI (kg/m²)

ECOG status 0
1
2
3

Haemoglobin (g/dl)

Platelets (x10⁹/l)

White cell count (x10⁹/l)

Neutrophils (x10⁹/l)

Lymphocytes (x10⁹/l)

CRP (Mg/L)

Creatinine (µmol/l)

Urea (µmol/l)

-Lung function

FEV₁ (% predicted)

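### The section 5.3 rule for conversion from VATS to open counts operations that were open from the outset and loses conversions that end without a lobectomy

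*SAP*

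**What the plan says.** Section 5.3 derives conversion from two items, allocation and the type of lobectomy received. It is YES "if allocated to VATS AND open lobectomy received", and otherwise "NO: if allocated to VATS AND VATS lobectomy received MISSING: otherwise".

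Protocol deviation 3 in the same section is YES for the VATS arm on "Allocation = VATS AND lobectomy received = open" and NO on "Allocation = VATS AND lobectomy received = VATS". Its only other branches concern the open arm. Section 3.3 describes this deviation as "Patient received the alternative intervention to that they were allocated (only includes patients who underwent a lobectomy"), and Table T1 reports it by arm. Deviation 2 is coded "YES: if lobectomy = NO NO: if lobectomy = YES MISSING: otherwise".

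Table T2 covers the VATS arm only. Its title refers to conversion to open surgery, not to open lobectomy, and its reasons are technical, anatomical and oncological problems. Table T5 lists pneumonectomy, segmentectomy, wedge resection and open-and-close alongside lobectomy.

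Deviation 4 in section 5.3 is YES above four ports or incisions, and "NO: if less than four ports/incisions used during procedure". Everything else is MISSING. T5 has a category for exactly four. Deviation 4 appears in neither section 3.3 nor T1.

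**The concern.** A conversion is an event during an operation: it starts thoracoscopically and is finished open. To identify one, a rule must know how the operation began. The section 5.3 rule knows only the allocation and how a lobectomy was done, so it identifies a different group of patients from the one T2 describes.

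The conversion rate tells readers how often the VATS approach could not be completed, and it is a basic companion to an intention-to-treat comparison of VATS with open surgery. A count that includes operations never attempted by VATS, and leaves out converted operations in which no lobectomy was done, does not answer that question.

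**Working it through.** The SAP states no figure for conversions, so there is none to reproduce. The check applies the section 5.3 rules literally to each possible surgical course of a VATS-allocated patient.

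| Surgical course (allocated to VATS) | Conversion | Deviation 3 | Deviation 2 |
|---|---|---|---|
| VATS lobectomy completed | NO | NO | NO |
| Begun as VATS, converted, open lobectomy | YES | YES | NO |
| Open from first incision, open lobectomy | YES | YES | NO |
| Begun as VATS, converted, pneumonectomy, wedge or segmentectomy | MISSING | MISSING | YES |
| Begun as VATS, converted, open-and-close | MISSING | MISSING | YES |
| VATS wedge, no conversion | MISSING | MISSING | YES |
| No surgery | MISSING | MISSING | YES |

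Four things follow.

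1. Conversion and deviation 3 agree in every row, so within the VATS arm they are one variable under two names.
2. Rows two and three are coded alike. A patient never operated on by VATS enters T2 as a conversion, and T2 has no reason row for VATS not attempted.
3. Rows four and five are true conversions to open surgery but are coded MISSING, exactly like a VATS wedge without conversion or no surgery at all. Section 6.2.8 shows missing categorical data through observation counts, so a reader would see a smaller denominator but not why.
4. The size of the error can be written down but not evaluated. Let a be the number converted with an open lobectomy, b the number open from the outset with a lobectomy, and c the number converted without a lobectomy. The rule counts a + b. The true number of conversions is a + c. The net error is (a + b) − (a + c) = b − c, which may be positive, negative or zero. The number of patients wrongly coded is b + c even when the totals agree. The SAP gives none of a, b or c.

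For deviation 4, the YES range is above four and the NO range is below four. Exactly four satisfies neither and becomes MISSING, although T5 tabulates it.

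**The case against.** The strongest reply is that nothing inferential depends on these variables. The main analyses are by intention to treat (section 3.5), the safety population is grouped by allocation (section 3.6), and no model in section 6.2 uses conversion or deviation 3. That stands, and it limits the point to descriptive tables.

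A reader might go further than the SAP allows in five ways.

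- **That counting conversions under deviation 3 is an error which overstates non-adherence in T1.** Section 3.3 defines the deviation by treatment received, and a VATS-allocated patient whose lobectomy was completed open fits that definition. The SAP may well intend it. What is missing is a way to tell the two kinds of patient apart.
- **That the section 3.6 safety footnotes carry the fault forward.** Section 3.6 does not refer to these derivations, and a note that a VATS-allocated patient received open surgery would be accurate for a conversion.
- **That the T2 reason "Requirement for sleeve resection" proves cases are lost.** T5 has a category for lobectomy with airway resection. A sleeve case recorded as a lobectomy would still be coded YES. The evidence for lost cases is T5's non-lobectomy categories.
- **That T1 and T2 become unreadable, or that patients disappear.** A converted patient without a lobectomy is still counted under deviation 2, in T1 and in T5. Only the T2 entry is lost.
- **That the distortion can be given as a rate or a multiple.** Any such figure would rest on invented counts.

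It is also fair that the case report form is not shown, so the coding of the lobectomy received after a conversion is unknown. This does not rescue the rule. If converted cases were recorded as VATS, the rule would return NO for every converted lobectomy. It can work only if they are recorded as open, which is the reading used above.

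On deviation 4, a count of YES would not change if four ports were MISSING rather than NO, and no skeleton table reports the item. It is a drafting error with little consequence.

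**Conclusion.** The conversion derivation is wrong as written. It includes operations that were open from the outset and omits conversions that end without a lobectomy, so it does not give the quantity that T2 is set up to report. This follows from the stated rules and needs no outside fact beyond the ordinary meaning of conversion, which T2's own list of reasons supports. It assumes that the recorded approach is the one by which the lobectomy was completed.

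The effect is confined to T1 and T2. In T2 the count is off by b − c, with b + c patients wrongly coded. In T1 the deviation 3 row is correct as a count by treatment received, but cannot be separated into its two components. No treatment-effect estimate changes. The four-port gap, and the absence of deviation 4 from section 3.3 and T1, are minor inconsistencies of the same section.

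**What to change.** 1. In section 5.3, derive conversion as YES if the patient was allocated to VATS, the operation was begun as VATS and it was completed open, whatever the final resection. Code NO if it was begun and completed as VATS. Give separate codes to open from the outset and to no surgery, so that MISSING means unknown. Use the operative record, or failing that the conversion reasons collected for T2.
2. Keep deviation 3 by treatment received if that is the intention, and say so. Split its VATS-arm row in T1 into intra-operative conversion and open from the outset.
3. In deviation 4, make NO the complement of the stated YES rule, that is, four or fewer ports or incisions. Then either add the item to section 3.3 and T1, or delete it from section 5.3.

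The cost is a few lines of SAP wording, the derivation code and one extra row in T1. No new data are needed if the operative record shows how the operation began. If it does not, the T2 reasons can identify conversions, provided they were also recorded for converted operations without a lobectomy. The documents do not show this, so it should be checked first.
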